### **5.2. Handling of missing data and drop-outs**

In case of missing data and drop-outs a complete case analysis is performed.

### **5.3. Randomization**

Randomization will be performed using the R sample function. 1:1 Randomisation will be performed in random block sizes of 4, 6 and 8. Randomisation will be performed automatically by the same sql script which is used for screening.

## **6 REGULATORY ASPECTS AND SAFETY**

### **6.1 Local regulations / Declaration of Helsinki**

This study is conducted in compliance with the protocol, the current version of the Declaration of Helsinki, the ICH-GCP. If the clinical trial is not conducted according to ICH-GCP guidelines, the paragraph above must be adapted accordingly (ClinO Art. 5, Abs 2), the HRA as well as other locally relevant legal and regulatory requirements.

### **6.2 (Serious) Adverse Events**

Due to the character of the invention, causal relationships between any Serious Adverse Event (SAE) or Adverse Event (AE) and the intervention can generally be ruled out.

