## 1 STUDY SYNOPSIS

Sponsor / Sponsor-Investigator	Name(s) and contact details of Sponsor / Sponsor-Investigator
Study Title	Impact of Semi-automated proposal and optimization of diagnoses and surgical procedures for precoding: a randomized controlled trial
Short Title / Study ID	Semi-automated Precoding
Protocol Version and Date	Version 2 (dated 24/05/2019)
Study Registration	Intended: https://clinicaltrials.gov/
Study Category and Rationale	Not applicable
Background and Rationale	In a DRG system, insufficient or incorrect coding negatively impacts reimbursement. Assuming the DRG system in use to be optimal, the quality and efficacy of treatment could be improved if reporting and demission are electronically controlled and adjusted to the DRG system in use. In the long term, a fair reimbursement might reduce the pressure on the staffing ratio and thus increase the patient safety.
Risk / Benefit Assessment	The participants are not exposed to any intervention. A more accurate reporting and a treatment more adherent to the pre-setting of the DRG system in use by specially trained physicians should not impose any risk to the participants.
Objective(s) and Endpoint(s)	
Primary endpoint:
 
 
• Total reimbursement per day of hospital stay
 
 
Secondary endpoints:
 
 
• Length of hospital stay
 
• Total reimbursement per case
 
• Case mix index
 
• Severity of perioperative complications
 
• Readmission rate (safety endpoint)
 

Study Design	monocentric, randomized two-arm un-blinded study
Statistical Considerations	Continuous data are analysed using non-parametric Mann-Whitney U-tests because of skewed distributions of the data. Categorical data will be analysed using Chi-square-statistics.
Inclusion- / Exclusion Criteria	All inpatients hospitalized at the department of surgery undergoing any surgical procedure not eligible for ambulant operation at the Kantonsspital St. Gallen are included. No exclusion of vulnerable patients is planned.
Number of Participants with Rationale	According to a simulation study, a total of 1200 patients and 600 patients per arm are needed to detect an increase of 5% in the reimbursement per day of hospital stay with a power of 90%.

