Study Intervention	In the intervention arm, reporting and the time of demission are crosschecked and corrected by physicians with special awareness of the DRG system during the hospital stay (preliminary precoding).
Control Intervention	In the control arm the coding for DRG grouping is performed after the patient's demission. Reports are not screened for conformability to the DRG coding system.
Study procedures	In the intervention arm, reporting and the time of demission are crosschecked and corrected by physicians with special awareness of the DRG system during the hospital stay (preliminary precoding).
Study Duration and Schedule	Planned 06/2019 of First-Participant-In Planned 01/2020 of Last-Participant-Out
Investigator	[name], Department of Surgery, Kantonsspital St. Gallen, St. Gallen, Switzerland E-mail: [contact] [contact]

Study Centre(s)	Kantonsspital St. Gallen, St. Gallen, Switzerland
Data privacy	No additional data exceeding the routine clinical data are generated. The electronic processing of these routine clinical data will be performed in the clinical database of the surgical department which is password-protected. As an additional measure of data privacy, only physicians involved in the study will be granted access to the results of electronic data processing.
Ethical consideration	The intervention assessed in this study consists of measures of quality control based on the DRG grouping. All data used for this study are already available to every physician involved in the treatment. For patients who are in the treatment group, treatment and reports are more extensively controlled by physicians. Thus the risk to overlook faults in documentation or treatment is likely to be reduced. If a more close implementation of the DRG Grouping transfers into less severe morbidity, a potential benefit for the participant would result.
GCP Statement	This study will be conducted in compliance with the protocol, the current version of the Declaration of Helsinki, the ICH-GCP, the HRA as well as other locally relevant legal and regulatory requirements.

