## 3.4. Study intervention

First, based on the randomisation list, for all patients randomized into the group with daily monitoring and optimization of DRG coding (treatment group), dedicated physicians control if all relevant diagnoses and procedures are correctly coded in the operation management software. If necessary, additional codable diagnoses and procedures are discussed with the operating surgeon and if appropriate the coding is changed accordingly. Finally, the internal coherence of the coding and the wording of the operation report are crosschecked. Therefore, the electronic signature procedure of operation reports will be adopted such that the report will not be sent before one of the dedicated physicians approved its final version.

Second, the dedicated physicians control if relevant diagnoses and procedures are correctly recorded in the drafts of the discharge reports. Therefore, patients in the treatment group are visited daily. In addition, the patient records are inspected and their relevance for the DRG coding is assessed. If necessary, relevant diagnoses are incorporated in the draft of the discharge report. Additionally, the matching between diagnoses and procedures listed in the discharge report is crosschecked. The optimal time of discharge of each patient is evaluated on a daily base.

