To support the process described above, for all patients randomized into the group with daily monitoring and optimization of DRG coding (treatment group), a pdf file with the current DRG grouping according to the procedures and diagnoses routinely coded in the Operation management software is created. Based on these procedures and diagnoses, the current DRG grouping status is estimated. Based on the estimated DRG grouping status, the actual length of stay is compared with the lower and upper limit and the mean length of stay determined by the associated actual DRG group. Additionally, based on routinely and systematically collected data in the clinical database of the surgical department, potential secondary diagnoses relevant for reimbursement are generated by computerized algorithms. For each potential secondary diagnosis, the hypothetical DRG Grouping considering the already coded procedures and diagnoses is estimated. The possible secondary diagnoses are deducted from laboratory measurements, from the extended Charlson comorbidity score routinely evaluated preoperatively by the department of anaesthesiology, and from the recording of perioperative complications.

Third, final discharge reports of patients randomized into the group with daily monitoring and optimization of DRG coding (treatment group), are controlled to ascertain the completeness of diagnoses and procedures and their concordance. Therefore, the electronic signature procedure of discharge reports will be adopted such that the report will not be sent before one of the dedicated physicians approved its final version.

In patients randomized into the control group none of the above described intervention steps will be performed. In these patients, the actual clinical routine will apply.

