#### Sample size calculation

Sample size calculation was performed in a separate simulation study using the total reimbursement divided by the length of hospital stay for the surgical department of the Kantonsspital St. Gallen in 2018. Sample size estimation was based on a two-sided significance level of  $\alpha = 0.05$  and a power of 90%. The increase in reimbursement was assumed to be 5% in the intervention group. Furthermore, in 15% of patients a shortening of the length of stay by one day was assumed in the intervention group. Randomization was 1:1. A drop-out rate of 10% was assumed. Based on this assumptions, a total of 1200 patients (600 per group) would be needed

to prove a significant increase in the total reimbursement divided by the length of hospital stay. According to the case load in 2018, the recruitment period would last 6 months.

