#### **Reporting of SAEs (see ClinO, Art. 63)**

All SAEs are documented and reported immediately (within a maximum of 24 hours) to the Sponsor-Investigator of the study.

If it cannot be excluded that the SAE occurring in Switzerland is attributable to the intervention under investigation, the Investigator reports it to the Ethics Committee via BASEC within 15 days.

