### **6.3 (Periodic) safety reporting**

One safety report is submitted once 3 Months after the starting date of the study to the local Ethics Committee by the Investigator (ClinO, Art. 43 Abs).

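### Section 6.2 presumes that adverse events are generally unrelated to the intervention, although the plan lets study physicians correct discharge timing and labels readmission a safety endpoint

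*Combined protocol and SAP*

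**What the plan says.** **The presumption.** Section 6.2 gives the character of the intervention as its only ground for stating that "causal relationships between any Serious Adverse Event (SAE) or Adverse Event (AE) and the intervention can generally be ruled out".

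**The reporting rule.** Under the next subheading, on reporting of SAEs, every SAE is documented and reaches the Sponsor-Investigator within 24 hours. The condition for a report to the Ethics Committee within 15 days is: "If it cannot be excluded that the SAE occurring in Switzerland is attributable to the intervention under investigation".

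**The intervention.** The synopsis says that reporting and "the time of demission are crosschecked and corrected by physicians with special awareness of the DRG system during the hospital stay". Section 3.4 adds: "The optimal time of discharge of each patient is evaluated on a daily base". To support this, "the actual length of stay is compared with the lower and upper limit and the mean length of stay" of the estimated DRG group.

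**The assumed effect.** In 5.1, "in 15% of patients a shortening of the length of stay by one day was assumed in the intervention group".

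**The safety outcome.** The synopsis marks readmission as a safety endpoint ("Readmission rate (safety endpoint"). Section 5.1 analyses it with a chi-square test. Section 3.2 describes a readmission list that is cross-checked with the randomisation list.

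**The concern.** An intervention confined to codes and reports could reasonably be presumed to have no causal link with adverse events. This one also acts on when patients leave hospital, and the plan counts on some of them leaving earlier. A complication or readmission after a changed discharge date is an event for which attribution should be considered, not set aside in advance.

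The judgement on attribution matters because it decides whether an individual SAE goes to the Ethics Committee. It is made in an un-blinded trial (3.3). A presumption carries most weight in borderline cases, and those are the cases for which the reporting condition exists.

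**Working it through.** The plan gives no figure for this point. The total of 1200 patients comes from a simulation on 2018 hospital data that the documents do not contain. It is not in dispute here. The check is mainly a comparison of the plan's own statements.

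**Step 1: does the design fit the presumption?**

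| Source | What it implies for causality |
|---|---|
| 6.2, opening statement | A link is generally ruled out, for any SAE or AE |
| Synopsis, study intervention | Discharge time is checked and corrected during the stay |
| 3.4 | Discharge time is evaluated daily; stay is compared with DRG limits and mean |
| 5.1, sample size | A shorter stay is expected in some intervention patients |
| Synopsis, endpoints | Readmission is watched as a safety outcome |
| Synopsis (ethics) and 7.2 | Less severe morbidity is named as a possible benefit |

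The first row does not fit the others. The last row shows an asymmetry: an effect on morbidity is entertained when favourable and generally ruled out when adverse.

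**Step 2: what does the presumption touch?** The Ethics Committee route depends on whether attribution can be excluded. The opening statement of 6.2 offers a general answer to that question before the facts of a case are known. Nothing in 6.2 says whether a readmission is among the events to be assessed.

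**Step 3: scale of the assumed change in discharge.**

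- Inputs from 5.1: 600 patients per group; 15% with a stay one day shorter.
- 0.15 × 600 = 90 intervention patients.

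This is the number of shorter stays that the plan assumes. It is not the number of patients to whom the presumption applies: the statement covers any SAE or AE, so it reaches all 600 intervention patients. It is not a count of events either.

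**Step 4: what would an interval for readmission show?** The documents give no readmission rate, so the rates here are assumptions. With 10% drop-out (5.1), 600 × 0.90 = 540 patients per arm are analysed. For a common rate p, the approximate 95% half-width of the risk difference is 1.96 × √(2p(1 − p)/540).

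| Assumed p | Half-width (percentage points) |
|---|---|
| 3% | 1.96 × √(2 × 0.03 × 0.97/540) = 2.0 |
| 5% | 1.96 × √(2 × 0.05 × 0.95/540) = 2.6 |
| 10% | 1.96 × √(2 × 0.10 × 0.90/540) = 3.6 |

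A chi-square p-value alone would not tell the reader that, at these rates, even an observed difference of zero leaves an increase of about 2 to 4 points compatible with the data.

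**The case against.** The best defence is that the opening statement of 6.2 is framing and the reporting rule below it governs. The word *generally* leaves room for exceptions. The rule covers every SAE and has a low threshold. By the plan's own assumption, 85% of intervention patients have no change in stay, and most steps in 3.4 concern codes and reports. The 15% is a sample size assumption and not a discharge target. There is other oversight too: daily morbidity and mortality analysis (4.2), daily discussion of readmissions (3.2), Ethics Committee access to source data (8.1 and 9) and a safety report at 3 months (6.3).

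All of this stands, and it keeps the point small. It does not justify the presumption, because the threshold is only as low as the judgement applied to it. It is also fair to say that a confidence interval does nothing for the causality judgement; it serves the randomised comparison of the safety endpoint.

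A reader might infer more than the documents support:

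- **That SAE reporting is missing or blocked.** It is neither; the rule in 6.2 is explicit.
- **That patients are to be sent home before they are ready.** No section says so. The comparison in 3.4 includes a lower limit, so the process is not described as running in one direction only.
- **That a special gap opens after month 3.** Section 6.3 says "One safety report is submitted once 3 Months after the starting date of the study", but not that this report lists individual events. The reporting rule in 6.2 is the only stated route for a single event to the Ethics Committee throughout, so splitting the trial at month 3 isolates nothing.
- **That the consent and insurance waivers fall.** Sections 4.2 and 6.8 rest on a similar premise, but whether the waivers are justified is for the sponsor and the Ethics Committee.

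**Conclusion.** The point holds as a minor correction of safety wording. The general presumption in 6.2 conflicts with an intervention that acts on discharge timing and with a safety endpoint chosen to watch for its consequences. An existing and sound reporting test is thereby given an unsupported starting point.

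The only size that the plan supports is the 90 of 600 intervention patients with an assumed one-day shorter stay, and that figure rests on the 15% assumption in 5.1. No estimate of harm or of unreported events can be made. The half-widths depend on assumed readmission rates and serve only to show why an interval is informative.

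**What to change.** 1. **Section 6.2:** delete the presumption. Let the existing test, whether attribution can be excluded, apply to each SAE on its facts. Name unplanned readmissions after discharge among the events assessed, using the readmission list already described in 3.2.
2. **Section 5.1:** report the readmission risk difference between arms with its 95% confidence interval beside the planned chi-square test.
3. **Sections 4.2 and 6.8:** check with the Ethics Committee that the statements that treatment is not interfered with and that study injury cannot occur remain consistent with the revised 6.2.

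Deletion is better than adding to 6.2 an explicit statement that the intervention influences discharge. Such a statement would clash directly with 4.2 and 6.8 unless they changed too.

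The first two changes cost a small amount of physician and analysis time. The third needs an exchange with the Ethics Committee and is not free if it reopens the grounds for the waivers. No endpoint, planned test, sample size or discharge process changes.

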#### **Reporting of SAEs (see ClinO, Art. 63)**

All SAEs are documented and reported immediately (within a maximum of 24 hours) to the Sponsor-Investigator of the study.

If it cannot be excluded that the SAE occurring in Switzerland is attributable to the intervention under investigation, the Investigator reports it to the Ethics Committee via BASEC within 15 days.

#### **Follow up of (Serious) Adverse Events**

Describe the follow up procedures of participants terminating the study with reported ongoing (S)AEs until resolution or stabilisation.

### **6.3 (Periodic) safety reporting**

One safety report is submitted once 3 Months after the starting date of the study to the local Ethics Committee by the Investigator (ClinO, Art. 43 Abs).

## **6.4 Radiation**

No radiation is performed in this study.

## **6.5 Pregnancy**

No reporting of pregnancies is planned.

## **6.6 Amendments**

Substantial changes to the study setup and study organization, the protocol and relevant study documents are submitted to the Ethics Committee for approval before implementation. Substantial amendments are changes that affect the changes in the protocol that affect study objective(s) or central research topic, changes of study site(s) or of study leader and sponsor (ClinO, Art. 29).

## **6.7 (Premature) termination of study**

Upon regular study termination, the Ethics Committee is notified via BASEC within 90 days (ClinO, Art. 38).

Upon premature study termination or study interruption, the Ethics Committee is notified via BASEC within 15 days (ClinO, Art. 38).

## **6.8 Insurance**

As no study-related damage or injuries can occur, no insurance is necessary.

# **7 FURTHER ASPECTS**

## **7.1 Overall ethical considerations**

The intervention assessed in this study consists of measures of quality control based on the DRG grouping. All data used for this study are already available to every physician involved in the treatment.

## **7.2 Risk-benefit assessment**

For patients who are in the treatment group, treatment and reports are more extensively controlled by physicians. Thus the risk to overlook a fault in documentation or treatment is likely to be reduced. If a more close implementation of the DRG Grouping transfers into less severe morbidity, a potential benefit for each participant can be assumed.

# **8 QUALITY CONTROL AND DATA PROTECTION**

## **8.1 Quality measures**

For quality assurance the sponsor or the Ethics Committee may visit the research site. Direct access to the source data and all study related files is granted on such occasions. All involved parties keep the participant data strictly confidential.

## **8.2 Data recording and source data**

The result of the screening and randomisation is documented in a read-only sql table in an already implemented clinical database of the department of surgery. In this password-protected database,

an audit trail is implemented. Data concerning primary and secondary outcomes are provided by the financial department upon request at the end of the study. No

### **8.3 Confidentiality and coding**

Trial and participant data will be handled with uttermost discretion and is only accessible to authorised personnel who require the data to fulfil their duties within the scope of the study. Participant identification data are protected from unauthorised or accidental disclosure, alteration, deletion, copying and theft by password protection, limited access to the database, hourly backup, and by hosting the database on an exclusive server without internet connection.

### **8.4 Retention and destruction of study data and biological material**

All study data are electronically archived for 10 after study termination or premature termination of the study.

## **9 MONITORING AND REGISTRATION**

No regular monitoring visits at the investigator's site are planned. Source data/documents are accessible to the sponsor or the Ethics Committee. Registration in a national language in the Swiss National Clinical trial Portal (SNCTP via BASEC) will be performed. In addition, the study will be registered at clinicaltrials.gov.

## **10. FUNDING / PUBLICATION / DECLARATION OF INTEREST**

No funding is planned. The findings will be published to an adequate peer reviewed journal with the following authorship:

[name], [name], [name], [name], [name], [name]

